#### ***Secondary objectives***

1. To explore and understand more detailed drug utilization patterns
  - o Standard doses versus reduced doses of NOACs

- Patterns of usage (i.e., switching, discontinuation) and clinical events preceding the pattern
- Compliance (i.e., medication possession ratio)

2. To compare effectiveness and safety of antithrombotic therapies versus not using therapies among low risk patients (low score of CHA2DS2-VASc)

**Study design:** Retrospective cohort study

**Population:** Subjects with atrial fibrillation diagnosed (from January 1, 2007 up to and including the index date\*) who newly initiated antithrombotic therapies (NOACs (not including edoxaban), warfarin, or used aspirin) between July 1, 2015 and November 30, 2016 in the Korean Health Insurance Review & Assessment Service (HIRA) database

*\*Index date is the first prescription date of study drugs, including NOACs, warfarin, and aspirin during the intake period (from July 1, 2015 to November 30, 2016).*

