**Table 1. Diagnosis codes for inclusion criteria.**

KCD-6 	KCD-7 
I48 (Atrial fibrillation and flutter)	I48 (Atrial fibrillation and flutter)
I480 (Atrial fibrillation)	I480 (Paroxysmal atrial fibrillation)
I481 (Atrial flutter)	I481 (Persistent atrial fibrillation)
	I482 (Chronic atrial fibrillation)
	I483 (Typical atrial flutter)
	I484 (Atypical atrial flutter)
	I489 (Atrial fibrillation and atrial flutter, unspecified)

KCD-6, Korean version of ICD-10 (6th revision); KCD-7, Korean version of ICD-10 (7th revision)

1) KCD-6 diagnosis codes will be used from 1 July 2015 to 31 December 2015.

2) KCD-7 diagnosis codes will be used from 1 January 2016 to 30 November 2016.

[NOTE] KCD code is based on ICD-10 and almost similar, but KCD code is slightly different from ICD-10 (e.g., ICD-10 is more subdivided and extensive than KCD code).

3. Patients prescribed aspirin, warfarin, or NOACs during intake period (from July 1, 2015 to November 30, 2016)

*[Note] NOACs include apixaban, dabigatran, and rivaroxaban.*

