### 8.2.2 Exclusion criteria

Patients meeting any of the following criteria will not be included in the study.

1. Medical claims indicating diagnosis or procedure for hip/knee replacement surgery within 6 weeks prior to index date
2. Medical claims indicating a diagnosis code indicative of rheumatic mitral valvular heart disease, mitral valve stenosis during the 12-month baseline period  
(Valvular AF / Prosthetic heart valves)
3. Medical claims indicating a diagnosis code of VTE (Venous thromboembolism) during the 12-month baseline period
4. Medical claims indicating a diagnosis or procedure code of transient AF, or cardiac surgery during the 12-month baseline period

(Thyrotoxicosis, Hypertrophic cardiomyopathy, Elective defibrillation, radiofrequency ablation, or left atrial appendage occlusion)

5. Medical claims indicating a diagnosis code of other conditions during the 12-month baseline period  
(End-stage chronic kidney disease / Kidney transplant / Dialysis / Pericarditis)
6. For the comparison of “NOAC versus NOAC”, and “NOAC versus warfarin”, patients with any OACs (apixaban, dabigatran, rivaroxaban, or warfarin) in the pre-index period (from 1 year prior to the day before index date)
  - *[NOTE] Patients prescribed antiplatelets in the pre-index period will not be excluded.*
7. For the comparison of “NOAC versus aspirin”, patients with following medications in the pre-index period (from 1 year prior to the day before index date)
  - NOAC user: OACs (apixaban, dabigatran, rivaroxaban, warfarin)
  - Aspirin user: none
  - *[NOTE] NOAC user is defined as OAC naïve user and aspirin user is allowed to have OACs or antiplatelets in the pre-index period.*

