Exclusion criteria	Exclusion criteria	HIRA database	
Claims with the following KCD codes or procedure codes:
 
 
1. Valvular AF/ Prosthetic heart valves: I05, I08, I09, I34, Q23, T820, T826, Z952, Z953, Z954            - Korean procedure codes: M6580, M6581, M6582, O1791, O1792, O1793, O1794, O1795, O1796, O1797, O1798, O1799, M6531, M6532, M6533, O1690, O1730, 1740, O1750, O1760, O1770, O1781, O1782, O1783, O1810, O1826
 
2. End-stage of chronic kidney disease/dialysis: N185, T824, Y602, Y612, Y622, Y841, Z49, Z992, E1022, E1122, E1222, E1322, E1422
 
3. Kidney transplant: Z940
 
4. Venous thromboembolism: I636, I676, I801, I802, I803, I808, I809, I81, I822, I823, I829, I26
 
5. Hip or knee replacement            - Korean procedure codes: N0711, N0715, N1711, N1715, N1721, N1725, N2070, N2072, N2077, N2710, N2712, N2717, N3710, N3712, N3717, N3720, N3722, N3727, N4710, N4712, N4717, N4720, N4722, N4727
 
6. Thyrotoxicosis: E05
 
7. Pericarditis: I30, I31, I32
 
8. Hypertrophic cardiomyopathy: I422
 
9. Elective defibrillation, radiofrequency ablation, or left atrial appendage occlusion            - Korean procedure codes: M5880, M6540, M6542, M6545, M6547, M6511
 

Follow-up period	Follow-up period	HIRA database	
From the index date until the first occurrence of the following whichever came first:
 
 
1. Discontinuation: maximum of a 30-day gap after the calculated time to finishing the pack based on pack size and number of tablets per day. Switching: switch to any other study drugs
 
2. Outcome occurrence
 
3. Study ends: November 30, 2016
 

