6. For the comparison of “NOAC versus NOAC”, and “NOAC versus warfarin”, patients with any OACs (apixaban, dabigatran, rivaroxaban, or warfarin) in the pre-index period (from 1 year prior to the day before index date)
 - *[NOTE] Patients prescribed antiplatelets in the pre-index period will not be excluded.*
7. For the comparison of “NOAC versus aspirin”, patients with following medications in the pre-index period (from 1 year prior to the day before index date)
 - NOAC user: OACs (apixaban, dabigatran, rivaroxaban, warfarin)
 - Aspirin user: none
 - *[NOTE] NOAC user is defined as OAC naïve user and aspirin user is allowed to have OACs or antiplatelets in the pre-index period.*

Cohorts

To avoid increasing type I error when multiple comparisons occur, this full analysis set will be splitted into multiple sub-analysis sets as follows:

1. NOAC vs NOAC (both as OAC naïve users)
 - A. Sub-dataset 1: patients with index treatment of apixaban and patients with index treatment of dabigatran
 - B. Sub-dataset 2: patients with index treatment of apixaban and patients with index treatment of rivaroxaban
 - C. Sub-dataset 3: patients with index treatment of dabigatran and patients with index treatment of rivaroxaban

[NOTE] The index date will be defined as date of the first prescription of NOAC in patients with NVAF. To identify new users, a look-back observation period from 1 year prior to the day before the index date will be used and must indicate no OAC use during this period. The diagnosis date of NVAF could occur from January 1, 2007 up to and including the index date.

2. NOAC vs warfarin (both as OAC naïve users)
 - A. Sub-dataset 4: patients with index treatment of apixaban and patients with index treatment of warfarin
 - B. Sub-dataset 5: patients with index treatment of dabigatran and patients with index treatment of warfarin
 - C. Sub-dataset 6: patients with index treatment of rivaroxaban and patients with index treatment of warfarin

[NOTE] The index date will be defined as date of the first prescription of NOAC or warfarin in patients with NVAF. To identify new users, a look-back observation period from 1 year prior to the day before the index date will be used and must indicate no OAC use during this period. The diagnosis date of NVAF could occur from January 1, 2007 up to and including the index date.

3. NOAC (OAC naïve user) vs aspirin (no restrictions of antiplatelet or OAC use in the pre-index period)

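### The OAC washout omits edoxaban, so prior edoxaban users count as OAC-naive, and the protocol and SAP label a change to edoxaban differently

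*Protocol*

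**What the plan says.** **Study drugs.** The Population paragraph of the protocol abstract (section 3) limits the cohort to initiators of "NOACs (not including edoxaban), warfarin, or used aspirin". Protocol 8.2.1 repeats the restriction: "NOACs include apixaban, dabigatran, and rivaroxaban".

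**Washout.** For NOAC versus NOAC and NOAC versus warfarin, criterion 6 in Protocol 8.2.2 removes "patients with any OACs (apixaban, dabigatran, rivaroxaban, or warfarin) in the pre-index period". For NOAC versus aspirin, criterion 7 names the same four drugs for the NOAC arm. For the other arm, "aspirin user is allowed to have OACs or antiplatelets in the pre-index period". SAP 3.1 carries the same lists. Its notes under Cohorts state the new-user condition generally: the one-year look-back "must indicate no OAC use during this period".

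**End of follow-up.** The follow-up row of Protocol 8.3 ends follow-up at the first of discontinuation, switching, outcome or study end. Discontinuation is a gap in index-drug supply. Switching is a "switch to any other study drugs". SAP 3.1 has the same end points. SAP 4.3, Table 3, defines a switch as a fill of an OAC other than the index drug within 30 days after discontinuation, and dates discontinuation at the end of the last index-drug supply before the gap.

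**The concern.** Not studying edoxaban as an exposure is a legitimate choice. Leaving it out of the washout is a separate matter. The washout exists so that the NOAC and warfarin arms contain people starting oral anticoagulation, and a patient who moves from edoxaban to a study OAC is not starting it. The plan itself treats edoxaban as a NOAC: the abstract has to carve it out by name, and the background cites the edoxaban-versus-warfarin trial among the NOAC trials.

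The washout governs both arms of sub-datasets 1-6 and the NOAC arms of sub-datasets 7-9, which serve primary objectives 2 and 3. The baseline medication list (SAP Table 4 and Table 12) contains no anticoagulant, so prior edoxaban use would not enter the propensity score as listed. If such patients were spread unevenly over the index drugs and had a different event risk, the hazard ratios would shift.

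The switching mismatch bears mainly on a secondary objective, the description of switching, discontinuation and the events preceding each. The same patient could be tabulated under different headings depending on which document the programmer follows.

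**Working it through.** The plan attaches no figure to this point, so there is nothing of its own to reproduce. The check compares the texts and then bounds the size under stated assumptions.

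**1. Who passes the washout.** Take a patient dispensed edoxaban within the year before a first study-OAC prescription.
- Criterion 6: the four named drugs are absent, so the patient is not excluded (sub-datasets 1-6).
- Criterion 7, NOAC arm: same list, same result (sub-datasets 7-9).
- Criterion 7, aspirin arm: no OAC restriction, so the omission changes nothing.
- SAP general condition (no OAC use in the look-back): met only if OAC is read as the four drugs.

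**2. Window.** Intake runs from 1 July 2015 to 30 November 2016 (519 days inclusive). The one-year look-backs therefore span 1 July 2014 to 29 November 2016.

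**3. A patient who stops the index drug and moves to edoxaban.**

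| | Protocol 8.3 | SAP 3.1 and 4.3 |
|---|---|---|
| Counted as a switch? | No: edoxaban is not a study drug | Yes, on a plain reading of OAC |
| Does follow-up end? | Yes, through discontinuation | Yes, through discontinuation or switching |
| Time after index supply ends that is charged to the index drug | At most 30 days, if the gap counts as exposed | 0 days |

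Under the SAP, a switch falls within 30 days after the discontinuation date. Calling it a switch changes the label and does not move the censoring date. Overlap between an early edoxaban fill and leftover index supply could add a little shared time.

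**4. Upper bound on the 30-day gap.** Assume a share p of patients changes to edoxaban, the average follow-up is T days, and all 30 days count. The share of person-time is 30p/(T + 30p).
- p = 1%, T = 365: 0.3/365.3 = 0.1%
- p = 5%, T = 90: 1.5/91.5 = 1.6%

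**5. Effect of the washout omission on the hazard ratio.** Let f be the share of prior edoxaban users in one arm (none in the other) and r their hazard relative to truly naive users. Neither is in the documents. Approximately, with the affected arm as numerator, observed HR / true HR = 1 + f(r - 1).

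| f | r = 0.5 | r = 2.0 |
|---|---|---|
| 0.5% | 1 - 0.005 × 0.5 = 0.9975 | 1 + 0.005 × 1 = 1.005 |
| 5% | 1 - 0.05 × 0.5 = 0.975 | 1 + 0.05 × 1 = 1.05 |
| 10% (beyond the working range) | 1 - 0.10 × 0.5 = 0.95 | 1 + 0.10 × 1 = 1.10 |

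If the affected arm is the reference, take the reciprocal: at f = 5%, 1/1.05 = 0.952 to 1/0.975 = 1.026. If f and r are equal in both arms, or no edoxaban was dispensed, the ratio is 1.

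**The case against.** The strongest defence is that the usage may be consistent. Both documents spell out OAC as four drugs in the exclusion criteria and the abstract removes edoxaban by name, so the SAP's general no-OAC condition may simply refer back to that list. Alternatively, if OAC has its ordinary meaning, the general condition already bars edoxaban. The same ambiguity reaches the SAP switching rule: if the four-drug list carries over, an edoxaban fill is not a switch there either. This stands to the extent that the text can be read two ways. It does not dispose of the point. The named list is what a programmer would implement, and no reason is given for treating prior edoxaban users as naive.

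The defence is also right on size. The documents do not say whether or how much edoxaban was dispensed in Korea in the relevant window, nor that prior users would differ between arms. Prior stroke and bleeding enter the planned propensity model through CHA2DS2-VASc and HAS-BLED, which would absorb part of any difference in risk. The final covariate list is also still open (SAP 5.1).

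A reader might infer from the protocol's switching rule that a change to edoxaban leaves the patient in follow-up, with edoxaban time accruing to the index drug. The documents do not support that. Discontinuation depends only on index-drug supply, whatever is taken next, and it ends follow-up in both documents. A patient who adds edoxaban while still filling the index drug would remain in follow-up, but that is an addition and not a change.

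**Conclusion.** The point holds in two parts. First, as written, the washout in both documents admits prior edoxaban users to the NOAC and warfarin arms as OAC-naive, contrary to the stated no-OAC condition in its ordinary sense. The aspirin arm is not affected. Second, the protocol and SAP definitions of a switch differ. A change to edoxaban is a discontinuation under the protocol and, on a plain reading, a switch under the SAP. This concerns the recorded reason and hardly touches exposed time.

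The size is unknown from the documents and probably small. The range of about 0.975-1.05 for observed/true HR rests wholly on the assumed share (0.5-5%), the assumed relative hazard (0.5-2.0), and all contamination falling in the numerator arm. It is a reason to correct the definition and does not show that any comparison is materially biased.

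**What to change.** - Add edoxaban to the OAC list in exclusion criteria 6 (both arms) and 7 (NOAC arm), in Protocol 8.2.2 and SAP 3.1. It need not become a comparison arm.
- Define OAC once in each document, so that the washout and the switching rule use the term in the same sense.
- Reconcile the switching definitions in Protocol 8.3 and SAP 4.3, Table 3, so that an edoxaban fill is handled and labelled the same way in both. State whether the 30-day gap counts as exposed time.
- Report, by index drug, how many patients the added name removes. That replaces the assumed share with a count.

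The cost is one drug name in two criteria of each document, an aligned definition, and a small loss of patients. No new data should be needed: Protocol 8.6 provides for all pharmacy claims of these patients from January 2007 to November 2016.

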CHA 2 DS 2 -VASC	Covariates	HIRA database	CHA 2 DS 2 -VASC as continuous data or dichotomous data. The score will be calculated using the following KCD codes (refer to SAP-Appendix 2, Table 9): 1. Congestive heart failure 2. Hypertension 3. Diabetes mellitus 4. Stroke/TIA/TE 5. Vascular disease 6. Age $\geq$ 75 7. Age 65-74 8. Sex (female)
HAS-BLED	Covariates	HIRA database	HAS-BLED as continuous data or dichotomous data. The score will be calculated using the following KCD codes (refer to SAP-Appendix 2, Table 10): 1. Hypertension 2. Abnormal renal function 3. Abnormal liver function 4. Stroke 5. Bleeding history or predisposition 6. Age $>$ 65 7. Antiplatelet or NSAID use 8. Alcoholism
Charlson Comorbidity Index	Covariates	HIRA database	Charlson Comorbidity Index as continuous data or dichotomous data. The index will be calculated using the following KCD codes (Refer to SAP-Appendix 2, Table 11): 1. Myocardial infarction 2. Congestive heart failure 3. Peripheral vascular disease 4. Cerebrovascular disease 5. Dementia 6. Chronic pulmonary disease 7. Rheumatic disease 8. Peptic ulcer disease 9. Mild liver disease 10. Diabetes without chronic complication 11. Diabetes with chronic complication 12. Hemiplegia or paraplegia 13. Renal disease 14. Any malignancy, including lymphoma and leukemia, except malignant neoplasm of skin 15. Moderate or severe liver disease 16. Metastatic solid tumor 17. AIDS/HIV

Variable	Role	Data source(s)	Operational definition
Medication use	Covariates	HIRA database	
It will be consisted of the following:
 
 
1. History of NSAIDs
 
2. History of antiplatelet
 
3. History of PPI
 
4. History of H2-receptor antagonists
 
5. History of antiarrhythmics
 
6. History of digoxin
 
7. History of statins
 

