2.2 STUDY OBJECTIVES

Primary objectives

1. To explore baseline characteristics and drug utilization patterns in patients with nonvalvular atrial fibrillation (NVAF) who newly initiated NOACs, warfarin, or used aspirin
 - Demographic and clinical characteristics: Age, sex, types of health insurance, CHA₂DS₂-VASc score, HAS-BLED score, Charlson Comorbidity Index score, etc.
 - Descriptions of index treatment: Types of medication received, index dose intensity
 - Drug utilization pattern: Each patient will be followed-up until the first treatment modification occurs, or study ends (November 30, 2016).
2. To compare effectiveness including hemorrhagic stroke, ischemic stroke and systemic embolism of antithrombotic therapies in patients with NVAF with the following antithrombotic therapies: NOACs, warfarin, and aspirin
 - Primary effectiveness outcome: Composite of hemorrhagic stroke, ischemic stroke, and systemic embolism
 - Secondary effectiveness outcomes: Individual outcome of hemorrhagic stroke, ischemic stroke, and systemic embolism
3. To compare safety of anti-thrombotic therapies in patients with NVAF with the following antithrombotic therapies: NOACs, warfarin, and aspirin
 - Primary safety outcome: Major bleeding including gastrointestinal bleeding or intracranial bleeding and other bleeding
 - Secondary safety outcomes: Individual outcome of major bleeding

[NOTE] comparative analyses will be performed contingent on a feasibility assessment based on the descriptive analyses.

Secondary objectives

1. To explore and understand more detailed drug utilization patterns
 - Standard dose versus reduced dose

- Pattern of usage (i.e., switching, discontinuation) and clinical events preceding the pattern
- Compliance (i.e., medication possession ratio)

2. To compare effectiveness and safety of antithrombotic therapies versus not using therapies among low risk patients (low score of CHA₂DS₂-VASc)

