 - A. Sub-dataset 7: patients with index treatment of apixaban and patients with index treatment of aspirin
 - B. Sub-dataset 8: patients with index treatment of dabigatran and patients with index treatment of aspirin
 - C. Sub-dataset 9: patients with index treatment of rivaroxaban and patients with index treatment of aspirin

[NOTE] The index date will be defined as date of the first prescription of NOAC or aspirin in patients with NVAF during the intake period (from July 1, 2015 to November 30, 2016). To identify NOAC users, a look-back observation period from 1 year prior to the day before the index date will be used and must indicate no OAC use during this period. However, OAC use or antiplatelet use during a look-back observation period from 1 year prior to the day before the index date will be allowed for aspirin users. The diagnosis date of NVAF could occur from January 1, 2007 up to and including the index date.

Each patient was followed until discontinuation or switching of index treatment, outcome occurrence, or study ends (November 30, 2016).

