5 STATISTICAL METHODOLOGY AND STATISTICAL ANALYSES

5.1 STATISTICAL METHODS

Descriptive Analysis:

- All outcome variables will be summarized descriptively through the tabular and graphical display of mean values, medians, ranges, and standard deviations for continuous variables of interest and frequency distributions for categorical variables.
- The proportion of antithrombotics (aspirin, clopidogrel, aspirin and clopidogrel combination, warfarin, NOACs) at index date will be examined.
- Appropriate tests (e.g., t-test, chi-square test) will be used based on the distribution of the measure. The $p < 0.05$ considered significant.

Multivariate Analysis:

Propensity score method

The estimation of propensity score will be performed to control for confounders in each sub-dataset: (1) each NOAC versus NOAC; (2) each NOAC versus warfarin; (3) each NOAC versus aspirin.

Propensity scores are estimated by logistic regression analyses that incorporate potential treatment predictors as independent variables and types of index treatment as dependent variable (e.g., apixaban=1, warfarin=0). Covariates in the logistic regression model will

include variables such as age, sex, CCI score, CHA₂DS₂-VASc score, HAS-BLED score, and comorbidities, but the final list of these covariates will be discussed and determined after reviewing the results of descriptive analysis of the pre-matched datasets. Further, we will report the *c*-statistic of the propensity score that indicates the degree to which the propensity score model discriminates between treated patients and untreated patients.

After estimation of propensity score, we will perform propensity score matching (PSM). 1:1 matching without replacement will be performed.

The populations would be first matched using PSM according to their index treatment. For these matched populations we should then explore the proposed subgroups by: making an assessment of patient numbers in the subgroups and checking that patient characteristics are still similar between the index treatments in the subgroups. If they are similar, then conduct interaction term analysis is being conducted to determine whether the treatment effect varies between the subgroups. If the populations are no longer similar in characteristics, then re-matching via PSM will be performed for the subgroups.

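### NOAC-versus-aspirin comparisons (sub-datasets 7–9): prior OAC use is barred in one arm and allowed in the other, and no named analysis accounts for it

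*Protocol*

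**What the plan says.** **Eligibility.** Under Protocol 8.2.2 criterion 7, a NOAC user is excluded for any use of apixaban, dabigatran, rivaroxaban or warfarin in the year before index. For aspirin users no drug is listed, and a note adds that the "aspirin user is allowed to have OACs or antiplatelets in the pre-index period". SAP 3.1 agrees. Its heading for sub-datasets 7–9 gives the aspirin arm "no restrictions of antiplatelet or OAC use in the pre-index period", and the note beneath says that for aspirin users "OAC use or antiplatelet use during a look-back observation period from 1 year prior to the day before the index date will be allowed". For NOAC versus NOAC and NOAC versus warfarin (sub-datasets 1–6), SAP 3.1 criterion 6 removes "patients with any OACs (apixaban, dabigatran, rivaroxaban, or warfarin) in the pre-index period" from both arms. SAP 2.2 describes the population as patients "who newly initiated NOACs, warfarin, or used aspirin", so aspirin patients enter on use and need not be starters.

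**Adjustment.** Protocol 8.3 lists seven medication-history classes, including "History of antiplatelet" but no OAC class. SAP Tables 4 and 12 list the same seven. SAP 5.1 names age, sex, the Charlson index, CHA2DS2-VASc, "HAS-BLED score, and comorbidities, but the final list of these covariates will be discussed and determined after reviewing the results of descriptive analysis". For matching, "1:1 matching without replacement will be performed"; covariate adjustment on the propensity score and IPTW are also planned. The subgroups named in SAP 3.2 are the two risk scores and index dose. The only sensitivity analysis is IPTW from a multinomial propensity model.

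**The concern.** In three of the nine comparisons, one arm is OAC-naive by rule and the other may contain patients who recently took an OAC and are now on aspirin. Patients who left an OAC may differ in stroke or bleeding risk from patients who never took one. If they do, the hazard ratio for both primary outcomes carries that difference as well as the drug contrast.

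The balance check would not show it. SAP 5.1 judges balance by standardized differences of the covariates against 0.1. If prior OAC use is not among the variables examined, every check can pass while this imbalance remains. The limitations in Protocol 8.9 do not mention it either.

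The issue is confined to OACs. Prior antiplatelet use is allowed in both arms and is a named covariate.

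**Working it through.** The documents give no share of aspirin users with a prior OAC, no event count and no effect size, so there is no figure to reproduce. Shares and hazard ratios below are assumed.

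**1. Who can be affected.** The Protocol abstract sets the index date at the first NOAC, warfarin or aspirin prescription from 1 July 2015. A patient indexed on aspirin then has no earlier OAC within the intake period, so any prior OAC predates 1 July 2015. The part of the one-year look-back that can contain an OAC is 12 months for an index date of 1 July 2015, about 6 months for 1 January 2016, and none from 1 July 2016.

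The SAP 3.1 note to sub-datasets 7–9 defines index by NOAC or aspirin only. Under that wording prior NOAC use is limited in the same way, but prior warfarin use is possible up to the day before index throughout intake. It is also an inference that long-term aspirin users are mostly indexed at their first prescription after 1 July 2015, when the window is widest.

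**2. Imbalance if nothing is done.** With 0 in the NOAC arm and share p in the aspirin arm, the standardized difference (SMD) = p / √(p(1−p)/2) = √(2p/(1−p)).
- SMD = 0.1 at p = 0.005/1.005 ≈ 0.5%
- p = 5%: 0.32; 10%: 0.47; 30%: 0.93

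**3. Prior OAC added to the propensity score, with IPTW.** No NOAC user can have a prior OAC, so prior-OAC aspirin users have propensity 0 and weight 1. With R = NOAC:aspirin size ratio, the weighted aspirin arm totals N_aspirin + N_NOAC, of which p·N_aspirin had a prior OAC. The weighted share is p/(1+R).
- p = 10%, R = 0.5, 1, 2: share 0.067, 0.050, 0.033
- SMD = 0.38, 0.32, 0.26, all above 0.1

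The SAP's stabilized weights multiply every aspirin weight by the same factor (1−PE), so the share is unchanged. Matching or trimming can balance prior OAC only by dropping these patients, and the SAP states no caliper.

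**4. Prior OAC in the Cox model.** A prior-OAC stratum contains aspirin users only and carries no information on treatment, so the hazard ratio comes from OAC-naive patients. In a simulated null example (15,000 per arm, p = 10%, prior-OAC hazard ratio 0.5, 1.41 or 2), adjustment, stratification and restriction agreed to three decimals: 1.002, 1.000 and 1.024, where the 1.024 is sampling noise common to all three. Omitting prior OAC gave 1.069, 0.956 and 0.912.

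**5. Illustrative size.** For rare events and a true hazard ratio of 1, the apparent ratio = 1/(1 + p(r−1)), where r is the hazard of prior-OAC relative to other aspirin users.

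| p | r = 0.5 | r = 2 |
|---|---|---|
| 10% | 1.05 | 0.91 |
| 20% | 1.11 | 0.83 |
| 30% | 1.18 | 0.77 |

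Stroke and bleeding history in the risk scores would absorb part of r. If half of log r is absorbed (residual r = 0.71 or 1.41), the formula gives 1.03 and 0.96 at p = 10%. A weighted check at p = 10% and R = 1, with assumed stroke history of 40% in prior-OAC versus 20% in other aspirin users and bleeding history of 25% versus 12%, gave a slightly wider 1.037 and 0.948. With no residual effect it gave 0.999, that is, essentially no bias.

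**The case against.** The strongest reply has four parts.

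- **The arm is meant to be unrestricted.** This stands. The Protocol and SAP agree, the objectives use the same wording, and the SAP log records the revision of criterion 7 as a substantial amendment. A reader might infer an oversight or a contradiction; the documents show neither.
- **The SAP leaves room to handle it.** This stands in part. The propensity list is open, and SAP 5.1 plans Cox stratification and leaves the Cox variables to model building. A reader might infer from the IPTW result that no planned method can deal with prior OAC use. That is wrong: the positivity failure is specific to weighting. But the SAP does not name prior OAC for any of these uses, so the route is open without being committed to.
- **The index-date rule keeps the share small.** It limits the share, and shares such as 30% may be unrealistic. It does not bring the share to zero, and it does less for warfarin under the SAP note.
- **The bias figures are assumed.** This stands. An SMD measures imbalance, and only the risk difference left after covariate adjustment biases the hazard ratio.

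The comparisons are also contingent on a feasibility assessment, so they may not be run.

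**Conclusion.** The point holds as a gap in pre-specification that is cheap to close. In sub-datasets 7–9, prior OAC use is fixed at zero in the NOAC arm and left free in the aspirin arm, and nothing named in either document adjusts for it, displays it or tests it. The hazard ratios for stroke/systemic embolism and major bleeding can therefore mix drug with OAC experience.

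The share affected, the direction and the size cannot be determined from the documents. The ranges above rest wholly on assumed shares, hazard ratios and absorption by the risk scores, and no bias at all is among the possibilities.

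Two stronger readings are tempting. One is that these three comparisons are biased in a known direction or invalid; no figure in the documents supports that. The other is that the OAC-naive aspirin arm must become the main analysis. That is a trade-off: it changes the target population away from aspirin as used, and it would still compare new NOAC users with a mix of new and continuing aspirin users.

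**What to change.** In SAP 5.1, pre-specify one of the following for sub-datasets 7–9, for both stroke/systemic embolism and major bleeding:

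- a sensitivity analysis that applies the same one-year OAC-free look-back to aspirin users, with the propensity score re-estimated in the restricted cohort; or
- adjustment for, or stratification on, prior OAC use in the Cox model.

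Report the result beside the main analysis, and state the share of aspirin users with a prior OAC. The unrestricted aspirin arm may remain the main analysis. Adding prior OAC to the propensity model alone is not enough where IPTW is used.

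**Cost.** One extra analysis per comparison and no new data, since the look-back is already applied to NOAC users. The restricted result applies only to OAC-naive aspirin users and may lose some precision. Under 1:1 matching the loss is about nil if aspirin users still outnumber NOAC users. If aspirin is the smaller arm, the log-hazard-ratio interval widens by 1/√(1−p): about 3%, 5% or 20% at p = 5%, 10% or 30%. IPTW and covariate adjustment would also lose these aspirin users.
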